### **6.6.2. Vital Signs Analyses**

Vital signs will be summarized according to Pfizer standards (note that baseline is defined as in [Section 3.4](#) in relation to actual treatment).

Changes from baseline in systolic blood pressure, diastolic blood pressure and pulse rate will be summarized by treatment and time. The number (%) of participants with maximum increases from baseline will be tabulated by treatment as defined in [Section 5.2.3](#). Numbers and percentages of participants meeting the categorical criteria will be provided and individual values listed in the study report.

No formal inferential statistics will be applied to the vital signs data.

### **6.6.3. Electrocardiogram Analyses**

ECGs will be summarized by visits. Categorical summary of ECGs will be presented according to Pfizer standards (note that baseline is defined as in [Section 3.4](#) in relation to actual treatment).

Changes from baseline for the ECG parameters QT interval, RR interval, calculated QTcF interval (using QT and RR interval), PR interval, and QRS interval will be summarized by treatment and time. QTcF will be derived using Fridericia's correction formula. The number (%) of participants with maximum increases from baseline will be tabulated by treatment as defined in the [Section 5.2.3](#). Numbers and percentages of participants meeting the categorical criteria will be provided and individual values listed in the study report.

No formal inferential statistics will be applied to the ECG data.

#### 6.6.4. Other Safety Data

##### 6.6.4.1. Platelet count

Raw data, changes from baseline, and percent changes from baseline will be summarized by treatment, and week as described in [Section 5.2.2](#).

- Figures from summary outputs
  - ✓ Box and whisker plots by treatment and by week will also be displayed to characterize the distribution of changes from baseline over time. Only box, whiskers, median, arithmetic mean, and outliers should be reported in this graphic.
  - ✓ Box and whisker plots by treatment and by week will also be displayed to characterize the distribution of percent changes from baseline over time. Only box, whiskers, median, arithmetic mean, and outliers should be reported in this graphic.
  - ✓ For participants with any after Day 1 (ie post-randomization) platelet count result of < 100,000/mm^3, individual plots with overlay of platelet count, aPTT, and INR up to Week 6 (include unplanned in chronological/continuous order – not categorical) will be generated, by treatment. To do so, real date as reported in e-data load from Covance will be used.
    - If possible, a figure containing 4x4 panels (1 panel per participant) by treatment will be created with LEFT Y-axis reporting platelet count and aPTT levels and RIGHT Y-axis reporting INR levels.

Two statistical analyses will be performed on platelets levels.

The first statistical analysis will be performed using change from baseline over time.

The second analysis will be performed using the natural-logarithmic transformation of relative change from baseline in order to report percent change from baseline.

Both analyses will be performed and reported as described in [Section 5.2.5](#).

- Statistical Outputs for changes from Baseline:
  - ✓ The LSMeans estimates, and 80% confidence interval for each treatment at each time-point,
  - ✓ Difference between the LSMeans for active treatment against placebo and the corresponding 80% confidence interval will be presented at each time point.

- ✓ Summary tables reporting MMRM outputs will include the number of participants included in the analysis.
- Statistical Outputs for Percent Changes from Baseline:
  - ✓ Adjusted geometric LSMeans estimates with 80% confidence interval for each treatment along with the translation in percent change (with their associated confidence interval) over time,
  - ✓ Ratio of adjusted geometric LSMeans estimates for each active treatment against placebo and the corresponding 80% confidence interval along with the translation in percent difference (with their associated confidence interval) over time.
  - ✓ Summary tables reporting MMRM outputs will include the number of participants included in the analysis.

#### 6.6.4.2. Estimated Glomerular Filtration Rate

Raw data, and changes from baseline will be summarized by treatment, and week as described in [Section 5.2.2](#).

The statistical analysis will be performed using the change from baseline as described in [Section 5.2.5\\_Ref41484348](#).

- Statistical Outputs:
  - ✓ The LSMeans estimates, and 80% confidence interval for each treatment at each time-point,
  - ✓ Difference between the LSMeans for active treatment against placebo and the corresponding 80% confidence interval will be presented at each time point.
  - ✓ Summary tables reporting MMRM outputs will include the number of participants included in the analysis.
- Figures from statistical outputs
  - ✓ Line Plot of LSMeans estimates and 80% confidence interval over time,
  - ✓ Line Plot of placebo adjusted LSMeans and 80% confidence interval over time.

#### 6.6.4.3. Additional Graphical Representation

A figure containing 4x4 panels (1 panel per participant) by treatment will be created with LEFT Y-axis reporting TG and FPG levels and RIGHT Y-axis reporting FPI and ApoC3 levels when triglycerides levels  $\geq 600$  mg/dL post dosing.

### 7. IRC REVIEW OF UNBLINDED SAFETY DATA (DURING STUDY CONDUCT)

*This study will use an IRC. The IRC will undertake periodic unblinded review of the safety data while the study is on-going. These reviews are envisioned, at a minimum, after approximately 33%, and 66%, of planned total sample size in Part 1 (and separately if conducted, Part 2), has been randomized. The IRC is independent of the study team.*

These reviews will include an assessment of the observed safety – using unblinded outputs.

### 7.1.1. Analyses and Summaries

For the planned unblinded safety reviews, IRC members will receive the following data summarized/analyzed by treatment along with the relevant data listings.

#### **Study conduct and Baseline characteristics of Population Randomized:**

- Study conduct issues (e.g., enrollment status, currentness of the database, time between randomization and first treatment, eligibility violations)
- Participant evaluation groups
- Demographic and other baseline characteristics

**Safety Data:** The Committee will monitor certain specific safety-related laboratory parameters, vital sign parameters, and treatment-emergent adverse events (TEAEs) as well as serious adverse events (SAEs including death) listings in an unblinded manner for overall frequency of events. To do so, the listings which will be provided include:

- TEAEs (and SAEs) leading to temporary discontinuation of dosing;
- TEAEs (and SAEs) leading to permanent discontinuation and withdrawal;
- The listing of individual TEAEs and SAEs;
- All instances of hyperglycemia, or platelet reduction, or hypertriglyceridemia leading to permanent withdrawal;
- Listing of Treatment emergent adverse events (TEAEs) as defined in section 6.6 of this SAP;
- Listings of SAEs/deaths and narratives requested from the safety database (ie, ARGUS or similar)
- eGFR values and laboratory parameters outlined in Table 2 of this SAP represent the minimum list of parameters which will be listed and provided to the committee.
- This list may be expanded depending on team blinded review.

The Committee will receive the distribution of participants over time whose values cross the boundaries (ie Flag and Alert levels separately) for each of the parameters included in Table 2 of this SAP.

Percent change from baseline in fasting lipid parameters (ie triglycerides, total cholesterol, direct LDL-C, VLDL, HDL-C, and derived non-HDL-C), fasting apolipoproteins (ie ApoA1, ApoBtotal, ApoB100, ApoB48, ApoC3, and ApoE), liver function parameters (ie ALT, AST, Total Bilirubin, GGT, and Alkaline Phosphatase), eGFR, and will be provided for review.

Change from baseline in glycemic parameters (ie HbA1c, FPI and FPG) will be provided for review as well.

The following graphical representations will be provided:

- Box and whiskers plots of percent change from baseline for parameters in Table 2, eGFR, fasting lipid parameters (see list above), fasting apolipoproteins (see list above), and liver function test.
- Box and whiskers plots of changes from baseline for glycemic parameters (see list above):

Individual vital signs (blood pressure and pulse rate) via a listing of the raw data as well as values meeting the criteria outlined in Table 3 of this SAP will be provided.

No formal statistical analyses (eg MMRM) will be performed on safety data, for purposes of IRC review of unblinded safety data.

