### 2.2.1. Clinical Overview

As of January 2020, safety and efficacy of DGAT2i alone or when coadministered with ACCi in the target patient population (ie, those with biopsy-confirmed NASH with liver fibrosis stage 2 or 3) has not been evaluated although clinical activity and effectiveness of DGAT2i alone and when coadministered with ACCi has been assessed in participants with NAFLD with dosing up to 6 weeks.

Across the clinical studies completed/concluded with DGAT2i alone (n=6 studies), ACCi alone (n=6 studies) and DGAT2i + ACCi (n=2 studies), 736 *unique* participants have been randomized, with 120 (16%) exposed to placebo, 161 (22%) exposed to DGAT2i alone, 407 (55%) exposed to ACCi alone, 44 (6%) exposed to DGAT2i + ACCi, and 4 exposed to metformin alone in the DGAT2i-Metformin DDI study. DGAT2i alone has been evaluated as single oral doses up to 1500 mg, repeated doses up to 1800 mg/day (administered Q8H) for up to 14 days, and repeated doses of 600 mg/day (administered Q12H) for up to 6 weeks. ACCi alone has been administered at single, oral doses up to 240 mg, repeated ( $\leq$ 14-days) doses up to 200 mg/day (administered QD and Q12H), and repeated ( $\leq$ 16 weeks) doses up to 50 mg/day (administered QD). DGAT2i + ACCi has been evaluated at a single coadministered dose level of 300 mg BID (DGAT2i) + 15 mg BID (ACCI).

DGAT2i alone *or* as DGAT2i + ACCi has been evaluated in six Phase 1 studies in healthy adults (with 132 participants randomized) and two studies (1 Phase 1 and 1 Phase 2a) in participants with NAFLD (with 148 participants randomized). ACCi alone has been evaluated in five Phase 1 studies in adults (with 151 participants randomized) and one Phase 2a, dose-ranging study in participants with NAFLD (n=305 randomized including 68% with Sponsor-defined presumed NASH).

Administration of DGAT2i alone has been found to be well tolerated with an acceptable safety profile with no special safety concerns identified. Upon repeated administration of DGAT2i, across the 20-fold dose range evaluated (ie, 90 to 1800 mg/day), TEAEs reported in  $\geq 7$  (3%) participants across all groups evaluated were headache (11%), diarrhea (6%), fatigue (5%), pruritus (4%), abdominal pain (3%), and nausea (3%). Upon repeated administration of ACCi, across a 100-fold dose range evaluated (ie, 2 to 200 mg/day), the all-causality TEAEs reported in  $\geq 1.5\%$  of participants were headache (9%), diarrhea (7%), hypertriglyceridemia (6%), and nausea (5%).

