Coadministration of DGAT2i + ACCi, based on completed toxicity studies in rats and monkeys, as well as completed clinical studies, does not afford any additional adverse findings above and beyond those identified with administration of ACCi alone. Thus, in the current study, any adverse clinical impact of the above findings are expected to be minimized through: (1) the proposed frequent visits to site to permit close oversight of participants' safety via medical monitoring of a range of clinical assessments including safety-related laboratory tests, 12-lead ECGs, vitals, assessment of AEs; (2) inclusion of provisions for management of glycemic control (refer to [Appendix 10.9](#)) and the 2 identified adverse reactions ie, increases in fasting serum triglycerides (refer to [Appendix 10.10](#)) and reduction in platelet count (refer to [Appendix 10.11](#)); **and** (3) institution of an independent, IRC (refer to [Section 9.5](#)) to undertake unblinded review of the safety data while the study is on-going.

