#### 3.5.3.2. ECG of Special Clinical Concerns

Individual participants' ECG outlined in Table 4 of special clinical concern, which align with the Pfizer standard criteria, will be summarized by treatment, as part of standard safety-related outputs.

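### SAP 7.1.1 plans no by-arm ECG or QTcF output for the unblinded IRC reviews, although it sends the parallel laboratory and vital-sign criteria

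*SAP*

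**What the plan says.** **What the IRC gets.** SAP 7.1.1 opens its list with "IRC members will receive the following data summarized/analyzed by treatment along with the relevant data listings". The scope sentence is "The Committee will monitor certain specific safety-related laboratory parameters, vital sign parameters, and treatment-emergent adverse events (TEAEs", followed by SAEs and deaths. The items then named are:

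- study conduct and baseline data;
- TEAE and SAE listings with narratives;
- Table 2 laboratory parameters and eGFR;
- lipids, apolipoproteins, liver tests and glycaemic values;
- a raw listing of blood pressure and pulse rate, where also "values meeting the criteria outlined in Table 3 of this SAP will be provided".

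Of eGFR and the Table 2 laboratory parameters, the SAP says that they "represent the minimum list of parameters which will be listed and provided to the committee". It allows that list to grow after a blinded review by the team.

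**What the plan says about ECG elsewhere.** SAP 3.2.2 puts 12-lead ECG in the secondary safety endpoint, beside laboratory tests and vital signs. SAP 3.5.3.2 provides that each participant's "ECG outlined in Table 4 of special clinical concern" is summarised by treatment, and SAP 6.6.3 plans those summaries for final reporting. Protocol 2.3.1 rests risk mitigation on clinical monitoring that includes "safety-related laboratory tests, 12-lead ECGs, vitals, assessment of AEs", and separately on unblinded IRC review.

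**What the IRC is for.** Under Protocol 6.6, an IRC recommendation can lead to an active dose being paused or stopped. Protocol 9.6 gives it the safety data in general and leaves detail to a charter, which is not among the documents available here.

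**The concern.** SAP Tables 2, 3 and 4 are built in parallel: each defines threshold criteria for one class of safety data. Two of the three go to the IRC and the third does not, with no reason given.

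A focus on identified risks would not explain the difference. Protocol 2.2.1 reports no clinically significant effect on blood pressure or on cardiac conduction intervals, yet blood pressure is sent and ECG is not. Nor does data availability explain it: in Protocol Table 1, as far as the extracted rows can be read, ECG and vital signs carry the same visit marks.

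At stake is whether the body that can recommend pausing a dose would routinely see a moderate QTcF effect confined to one arm while others are still being randomised to that arm, and before Part 2 doses are chosen. Prior experience with the combination is small, with "44 (6%) exposed to DGAT2i + ACCi" at a single dose level.

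**Working it through.** The core of the point is textual. The plan gives no figure for ECG detection, so there is none to reproduce. The arithmetic below only sizes the gap.

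**1. Which ECG findings have another route to the IRC?** The IRC receives all individual TEAEs and SAEs, so the comparison is between SAP Table 4 and the QTcF criteria in Protocol Appendix 10.7.

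| Finding | SAP Table 4 | Appendix 10.7 |
|---|---|---|
| QTcF >450 to 480 msec | mild | not a criterion |
| QTcF >480 to 500 msec | moderate | may be an AE |
| QTcF >500 msec | severe | may be an SAE |
| Rise of 30 to under 60 msec, value at or below 480 | 30-60 category | not a criterion |
| Rise of 60 msec or more | 30-60 category at exactly 60, severe above 60 | may be an AE |

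The first and fourth rows meet a Table 4 category without meeting an Appendix 10.7 QTcF criterion. For the others, the appendix says only that they may qualify.

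**2. Size of the two looks** (Protocol 9.2.1 and 9.6: about 90 randomised to 5 equal arms, reviews at about 33% and 66%).

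- 0.33 x 90 = 29.7, and 29.7 / 5 = 5.9, about 6 per arm.
- 0.66 x 90 = 59.4, and 59.4 / 5 = 11.9, about 12 per arm.

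These count participants randomised. Fewer will have had an on-treatment ECG.

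**3. How well would AE reporting reveal a shift?** Assumptions, not in the documents: QTcF change is normal with SD 10 to 20 msec, and all 12 participants in an arm have an on-treatment ECG. The chance that any of 12 rises by at least 60 msec is 1 - (1 - p)^12, where p = 1 - Φ((60 - shift) / SD).

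- Shift 20, SD 10: p = 1 - Φ(4) = 0.00003, so 0.04%.
- Shift 20, SD 20: p = 1 - Φ(2) = 0.0228, so 24%.
- Shift 10: from under 0.01% (SD 10) to 7% (SD 20).

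For QTcF above 480 msec, assume also a baseline mean of 420 and SD of 20 msec, so that p = 1 - Φ((480 - 420 - shift) / √(SD² + 20²)).

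- Shift 20, SD 10: p = 1 - Φ(40 / 22.4) = 0.037, so 36% for any of 12.
- Shift 20, SD 20: p = 1 - Φ(40 / 28.3) = 0.079, so 63% for any of 12.

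So single outliers can well reach the IRC if investigators report them. The shift itself mostly would not show.

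**4. What would a by-arm summary resolve?** Half-width of the 95% interval for arm minus placebo = 1.96 x SD x √(2/n).

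- n = 6: 11.3 (SD 10) to 22.6 msec (SD 20).
- n = 12: 8.0 to 16.0 msec.

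Power for a 20 msec shift (two-sided 5%) is 41% to 93% at 6 per arm and 69% to 100% at 12. For 10 msec it is 14% to 41% and 23% to 69%.

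**5. What does prior experience exclude?** If none of the 44 had an event of a given ECG category (an assumption), the one-sided 95% upper limit for its rate is 1 - 0.05^(1/44) = 6.6%.

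**6. The QTcF formula.** SAP 3.5.3.2 divides QT by the cube root of RR, with RR stated in msec. For QT 400 and RR 1000 msec, 1000^(1/3) = 10 and 400 / 10 = 40 msec. With RR in seconds, 1^(1/3) = 1 and the result is 400 msec.

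**The case against.** The strongest reply is that the IRC is not cut off from ECG. It receives every TEAE and SAE unblinded, and marked QTcF prolongation may be reported as either. Protocol 9.6 does not exclude ECG, its two reviews are a minimum, and the charter may provide ECG output. Protocol 4.2 adds a monthly blinded review that can trigger a further unblinded one, and Appendix 10.7 recommends core-laboratory ECG alerts to the investigator and the sponsor's study team. SAP 7.2 unblinds some people outside the study team at about 50% of Part 1 data, and they may consider any Section 3 data, which includes ECG.

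The prior evidence is also wider than 44 people. Protocol 2.2.1 counts 161 on DGAT2i alone and 407 on ACCi alone, with no clinically significant conduction effect reported. The combination dose already tested (600 mg/day with 30 mg/day) equals or exceeds every Part 1 arm in total daily dose of each agent.

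Finally, ECGs are single recordings, and the extracted visit row shows no mark at Week 2 or Week 4. With so few participants per arm, a summary would resolve little.

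Much of this stands, and it limits the consequence. It does not fill the gap. The minimum-list sentence covers eGFR and laboratory parameters, and expansion depends on a blinded review, which cannot see a difference between arms. The monthly review and the core-laboratory alerts have the same limit. The PK/PD analysts are unblinded for modelling, their access to ECG is optional, and they have no stated safety role.

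**Conclusion.** The point holds as a modest gap. SAP 7.1.1 plans no by-arm ECG output for the IRC, so an arm-level QTcF shift, or a cluster of 30 to under 60 msec rises at or below 480 msec, would not routinely be seen there during the study except through reported AEs and SAEs.

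A reader might infer that nobody independent of the study team could see such a shift, or that the IRC receives no ECG information at all. The documents support neither: outliers can arrive as AEs or SAEs, unblinded PK/PD staff may look at ECG data, and the charter cannot be checked. What is established is absence from SAP 7.1.1, not absence from everything the IRC sees.

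The size is small. With about 6 and 12 randomised per arm, only large shifts or clusters would be visible even after the fix. The detection figures rest on an assumed SD of change of 10 to 20 msec and, for the 480 msec threshold, on an assumed baseline. That Week 6 is the only on-treatment ECG is read from a table damaged in extraction and needs confirming.

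**What to change.** Add to SAP 7.1.1, for each IRC review in Part 1 and, if conducted, Part 2:

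- a by-treatment count and a listing of participants meeting the Table 4 QT/QTcF criteria;
- a by-treatment box plot of change from baseline in QTcF, with PR and QRS if wanted, at the visits where ECGs are collected.

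If the IRC charter already provides this, a citation of the charter section in SAP 7.1.1 is enough.

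Before programming, correct the RR unit in the SAP 3.5.3.2 formula. As written it gives values ten times too small, which would make the Table 4 counts meaningless.

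The cost is slight extra programming per review. The ECGs are already collected and Table 4 summaries by treatment are already planned for the final report. Because each look is small, the output is best read as a screen for large shifts or clusters.

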## 7.2. Planned Interim Analysis Post Part 1 (and before start of Part 2)

*Interim analyses will be performed after completion of Part 1 to determine whether to conduct Part 2 and if so, guide selection of doses of DGAT2i and/or ACCi to evaluate in Part 2. Interim analysis results may be used to conduct a sample size re-estimation (eg, observed variability in Part 1 is higher than assumed for derivation of sample size for Part 1), facilitate PK/PD modeling, and internal business decisions regarding planning of future trials with DGAT2i and/or DGAT2i+ACCi.*

*A limited number of individuals not on the study team will be unblinded according to Sponsor SOPs with the purpose of composing PK/PD analysis sets and conducting PK/PD analysis. Data draws are expected at approximately 50%, and 100% of total study data from Part 1. These data are expected to include the primary endpoint (MRI-PDFF), plasma PK for DGAT2i and ACCi, fasting serum lipid parameters including fasted serum triglycerides (and fasted serum apolipoproteins, if available). Other data outlined in Section 3 may also be considered. The PK/PD analysis output at the completion of Part 1 (ie, achievement of LPLV in Part 1) will be shared as part of the planned Interim Analysis with selected members of the Sponsors' study team to enable decision to conduct Part 2 and if so, the dose(s) and dosing regimen(s) of DGAT2i + ACCi evaluated in Part 2.*

## 9. APPENDICES

### Appendix 1. Summary of Efficacy Analyses

Endpoint	Estimand Strategy	Statistical Method	Model/ Covariates/ Strata	Missing Data	Interpretation
Percent Change from Baseline in % Liver Fat assessed by MRI-PDFF at Week 6	Estimand 1	ANCOVA on log-transformed relative change	Treatment as fixed effects with log(baseline) as covariate.	No Imputation	Primary Analysis
Percent change from Baseline in Fasting Serum Triglycerides Over Time	Estimand 2	MMRM on log-transformed relative change	Treatment, week and treatment-by-week interaction as fixed effects, participant as random effect with log(baseline) as covariate.	No Imputation	Secondary Analysis
Tertiary endpoints: Percent change from Baseline over time	Estimand 2	MMRM on log-transformed relative change	Treatment, Week and Treatment-by-Week interaction as fixed effects, participant as random effect and log(baseline) as covariate.	No Imputation	Tertiary Analysis
Tertiary endpoints Percent Change from Baseline at Week 6	Estimand 1	ANCOVA on log-transformed relative change	Treatment as fixed effects with log(baseline) as covariate.	No Imputation	Tertiary analysis
Tertiary endpoints: Change from Baseline over time	Estimand 3	MMRM on change from baseline	Treatment, Week and Treatment-by-Week interaction as fixed effects, participant as random effect and baseline as covariate	No Imputation	Tertiary analysis

